	6.4 Description of procedures and measurements	16
	6.4.1 Participant Information and Consent.....	17
	6.4.2 Medical history.....	17
	6.4.3 Vital Signs	17
	6.4.4 Anthropometric measurements	17
	6.5 Data collection and storage	17
	6.6 Sample transport	18
	6.6.1 Blood samples processing	19
7	Adverse event program.....	19
	7.1 Subject premature Withdrawl	19
	7.1.1 Adverse Events.....	19
	7.1.2 Serious Adverse Events.....	20
8	Insurance and Indemnity.....	20
9	Reimbursement.....	20
10	Data management.....	20
11	Statistical analysis	21

12	Duration of Project.....	21
13	Administrative considerations	21
13.1	Changes to the conduct of the study/Amendments to study protocol.....	21
14	Ethical and Regulatory Considerations	21
15	Premature termination of the study	22
	Bibliography	23
	How anxious do you feel?	25
	How stressed do you feel?	25
	How sick/Nauseated do you feel?	25
	How dizzy do you feel?	25
	How flushed do you feel?	25

1 Summary

Obesity is a chronic disease that has become a major nutritional health problem worldwide.

When we eat food we feel more full, but different foods with the same energy value can induce a variable amount of fullness. We previously showed that foods that have higher protein content increases fullness the most. We have also previously shown that many of the signals that induces fullness comes from the lower part of the small bowel when natural hormones such as Peptide YY (PYY) and glucagon like peptide 1 (GLP-1) is released from endocrine cells within the bowel. Our hypothesis is that the intake of mixed meals containing natural protein, fats and carbohydrates will result in more satiety gut hormones (PYY, GLP-1) when these foods can bypass the digestion processes in the upper gut, but rather be fully digested in the lower gut. To achieve this we can use microcapsules made of natural protein only which will protect the food from digestion in the upper gut. These protein capsules will release the food in the lower gut and generate maximum stimulation of the satiety gut hormones. The higher functions of the brain will respond to these strong neuroendocrine signals by ensuing fullness

The current study will provide important information on the physiological function when digestion of foods is moved from the upper to the lower small bowel as regards postprandial satiety, and food intake.

Methods: Ten healthy volunteers, aged 18 to 65 years will be recruited. Each subject will be studied on six occasions one week apart. Prior to each study day, the subjects will consume an identical meal between 19.00 and 20.00 on the night before and refrain from alcohol and strenuous exercise for the 24 hours before and after each study day.

Subject will arrive to the Clinical Research Centre at St Vincent University Hospital at 08.30 having fasted the night before from 20.00. At 9:00 am a cannula will be inserted into the antecubital vein of the forearms. About 5 mL (1 teaspoon equivalent) will be taken to measure baseline hormone level. Another blood samples will be taken every 30 minutes thereafter. At 12:00, a final blood sample will be withdrawn and the cannula will be removed (total blood samples 7).

They will be asked to answer a questionnaire regarding your feeling of hunger, satiety and if there is any nausea on a linear scale. Then a drink containing 200 grams of macronutrient microcapsules suspension equating to 1087 kcal will be offered.

In a randomized way all subjects will receive a mixed meal containing 200 grams of macronutrient microcapsules suspension equating to 1087 kcal in their successive weekly visits:

- Option 1 High protein mixed meal in capsules that break down in the stomach,
- Option 2 High protein mixed meal in capsules that break down in the distal small bowel,
- Option 3 High fat mixed meal in capsules that break down in the stomach,

- Option 4 High fat mixed meal in capsules that break down in the distal small bowel,
- Option 5 High CHD mixed meal in capsules that break down in the stomach,
- Option 6 High CHD mixed meal in capsules that break down in the distal small bowel.

After 3 hours (i.e. at 12:00) participants will be offered standard *ad libitum* meal to measure their food consumption and another blood sample will be drawn. All subjects will be asked to rate their appetite on a Visual Analogue Scale (VAS) (see appendix B). Upon VAS completion the subjects will be allowed to go home.

Blood sample will be withdrawn from participants at the beginning and at the end of each visit. These samples will be used to quantify gut hormone levels

Conclusion:

The current study will provide important information on the physiological function of protein supplement on increasing postprandial satiety, reducing appetite and food intake. Understanding the underlying neuroendocrine signalling pathway that translate the exposure of intestinal lumen to macronutrients into a healthier eating behaviour will facilitate the development of food products that will have considerable implications on controlling food consumption and managing overweight and obesity.

2 Overview

The worldwide prevalence of overweight and obesity is expected to reach 57.8% by 2030. A considerable amount of evidence supports the belief that bariatric surgery is the most effective weight-loss intervention.

The global, rapidly increasing prevalence of overweight and obesity has triggered research into food or food products that have therapeutic potential in the management of overweight and obesity. Nutrition, along with physical activity and behavioural changes, are cornerstones of obesity and T2D management. The nutrient composition of ingested food and meals varies substantially between individuals and within the same individual over time. Macronutrient composition of the diet has been shown to influence appetite and metabolic responses. Sustained satiety is a key component in the therapeutic approach to induce a negative energy balance and to promote weight loss.

Our hypothesis is that the altered exposition of the proximal small bowel to high protein microcapsules will increase satiety and would help developing natural protein formulas that would induce maximal anorexic effect.

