The goal of the present study is to investigate the physiological effect of natural macronutrients when delivered exogenously to the proximal and distal small bowel. This will mimic some aspects of the physiological changes after Roux-en-Y gastric bypass. The oral administration of macronutrients in a protective capsule will enable us to deliver them to the proximal or the distal part of the small intestine depending on the chemical and physical properties of the capsules. Our study will provide important information on the physiological role of protein, fat, and carbohydrate content of the ingested food on specific gut hormone secretion and their effects on satiety

3 Potential side effects and risks

Blood sampling can cause mild pain and/or bruising. A doctor or a trained phlebotomist will insert this with experience in obtaining blood samples to minimise the discomfort caused. We do not expect any severe side effects

4 Study hypothesis

The delivery of high protein supplement to the proximal and distal gut will increase the release of anorexigenic gut hormones that have powerful satiety effect and will reduce food intake.

5 Study Objectives and Design

5.1 Primary Aim:

To identify the physiological satiety gut hormone response and the satiety response of subjects when macronutrients are digested in the distal rather than proximal small bowel.

5.1.1 Objective 1:

To quantify the physiological gut hormones response of differential macronutrient delivery to the proximal and distal small bowel.

5.1.2 Objective 2:

To quantify the physiological satiety response of differential macronutrient delivery to the proximal and distal small bowel.

5.1.3 Objective 3:

To quantify the amount of food consumed after a preload of differential macronutrient delivery to the proximal and distal small bowel.

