5.5.1 Design (10 subjects)

5.5.2 Macronutrient microcapsules

- The microcapsules will be stored in line with manufacturer instructions.
- As the study drug will be blinded to the research investigator
- The Microcapsules will be introduced by the research nurse and labelled with the appropriate code drink A, B, C, D, E or F.
- It will be given at 9:00 am on an empty stomach prior to the meal.

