5.5.3 Study procedures

At the screening visit a doctor or nurse will then perform the following tests and procedures to determine if the subject is eligible for the study:

- Medical history
- Physical examination
- Body measurements including height, weight and waist circumference
- Record of your medications or illnesses
- Urine pregnancy test (if applicable)

Visit 1-6 (1 week apart):

Subjects will be randomised to consume a one the 6 microcapsules in each week. Internet-based randomisation software will be used to allocate microcapsules to each subject at each visit

Eligible subjects will be invited to six consecutive visits in the clinical research centre at St Vincent University Hospital. On each occasion we would request you to have identical meals the night before between 19:00 and 20:00 hours and fast thereafter. Please refrain from alcohol and strenuous exercise for 24 hours before each study visit.

1. Food intake for the 24 h before each study day should be similar.
2. Participants will be asked to consume an identical meal between 19.00 and 20.00 on the night before each study (fish or pasta meal).
3. They will also be asked to be fasted and drink only water from 20.00 the night before the study.

In each visit, participants will be asked to be in the clinical research centre at 8:30. At 9:00 am a cannula will be inserted into the antecubital vein of the forearms. About 5 mL (1 teaspoon equivalent) will be taken to measure baseline hormone level. Another blood samples will be taken every 30 minutes thereafter. At 12:00, a final blood sample will be withdrawn and the cannula will be removed (total blood samples 7). They will be asked to answer a questionnaire regarding your feeling of hunger, satiety and if there is any nausea on a linear scale. Then a drink containing 200 grams of macronutrient microcapsules suspension equating to 1087 kcal will be offered. At 12:00 an *ad libitum* meal will be offered. After the meal they will also be provided with a similar questionnaire to fill in, in order to establish your fullness and satiety level. The total visit time is around five hours and there is a total of approximately 35 ml of blood (less than 2 table spoons) at each visit 1 to 6.

6 Methodology

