6.3 Visit and procedures

Table 1: Schedule of Study Visits and Events

Trial Periods	Screening	V1	V2	V3	V4	V5	V6	Premature discontinuation	Follow up/ Premature discontinuation
Timing of visit (weeks)	-1	1	2	3	4	5	6		
Informed Consent	X								
Eligibility Assessment	X								
Record medications and illnesses	X							X	X
Anthropometric Measurements	X							X	X
Blood Samples		X	X	X	X	X	X		
Randomisation		X	X	X	X	X	X		
Visual Analogue Scales		X	X	X	X	X	X		
Adverse events		X	X	X	X	X	X	X	X

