6.4.4.4 Visual analogue Scales

Visual analogue scales will be used to assess subjective feelings of malaise, nausea and symptoms of flushing (Appendix B)

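### No readable form asks about lower-gut symptoms after drinks designed for distal release, and the follow-up after Visit 6 has no date

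*Combined protocol and SAP*

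**What the plan says.** **Timing.** Section 5.5.3 states "participants will be asked to be in the clinical research centre at 8:30". Section 5.5.2 says of the drink "It will be given at 9:00 am on an empty stomach prior to the meal". The Summary puts the test meal three hours later: "After 3 hours (i.e. at 12:00) participants will be offered standard". After the meal a visual analogue scale is completed, and then "Upon VAS completion the subjects will be allowed to go home". Section 5.5.3 adds "The total visit time is around five hours". Visits are one week apart.

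**What subjects are asked.** The Summary and section 5.5.3 describe ratings of hunger, satiety or fullness, and nausea. Section 6.4.4.4 says the scales will "assess subjective feelings of malaise, nausea and symptoms of flushing". The readable items in Appendix B are anxious, stressed, sick or nauseated, dizzy and flushed.

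**Stated risks.** Section 3 covers pain and bruising from blood sampling, then says "We do not expect any severe side effects". It does not mention the drinks.

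**Adverse events and illnesses.** Table 1 (section 6.3) marks adverse events at Visits 1 to 6, at premature discontinuation, and in a column headed "Follow up/ Premature discontinuation", which carries no week. Sections 7.1.1 and 7.1.2 require every adverse event to be entered in the case report form and the log. They also require the principal investigator to be told within 24 hours of the research investigator learning of it. Section 6.3.2.1 lists recording of medications and illnesses at Visits 1 to 6, and section 6.4.2 asks for the medical history to be updated at follow-up visits. Table 1 marks that row only at screening, discontinuation and follow-up.

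**The concern.** The design moves digestion of a large mixed meal from the upper to the lower gut in half of all exposures. Lower-gut discomfort is a plausible effect of that change and could differ between the stomach-release and distal-release versions. Yet the only gastrointestinal symptom asked about by name is nausea. Supervision ends a few hours after the drink, and no diary, call or next-day contact is described.

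Two things are at stake. The first is a complete safety record for each drink in a study whose stated purpose includes helping to develop food products. The second is prompt reporting: the 24-hour notification period starts when staff become aware, so an event recalled late is also reported late.

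**Working it through.** **1. Time on site after the drink**
- Inputs: arrival 08:30 and visit length about 5 h (section 5.5.3); drink at 09:00 (section 5.5.2).
- Check of the drink time: 12:00 meal − 09:00 = 3.0 h, which agrees with the Summary.
- Departure: 08:30 + 5 h = 13:30. Time after the drink: 13:30 − 09:00 = 4.5 h.
- Range: 4.0 to 5.0 h if about five hours means 4.5 to 5.5 h. With a 5 h visit, it is 4.0 to 4.25 h if cannulation, the baseline sample and the questionnaire delay the drink by 15 to 30 minutes (assumed).

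**2. Time to the next scheduled contact**
- After Visits 1 to 5: 7 × 24 − 5 = 163 h from departure to the next arrival.
- After Visit 6: undefined, because the follow-up column has no week.

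**3. Exposures affected**
- Planned drinks: 10 subjects × 6 = 60. Distal-release drinks: 10 × 3 = 30.
- Followed by a visit one week later: 10 × 5 = 50. Relying on the undated follow-up: 10/60 = 17%.

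**4. Can the under-recording be sized?** Only by assuming every rate. Suppose a lower-gut symptom follows 10% of distal drinks, direct questioning captures all of them, and general enquiry a week later captures 30% to 50%.

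| Assumption about clustering | Chance of recording none, asked directly | Chance of recording none, 50% to 30% captured |
|---|---|---|
| 30 independent drinks | 0.90^30 = 4% | 0.95^30 = 21% to 0.97^30 = 40% |
| 10% of subjects affected, after all three of their distal drinks | 0.90^10 = 35% | 40% to 51% |

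For the right-hand cell of the second row, a subject contributes at least one record with probability 0.1 × (1 − 0.5³) = 0.0875, or 0.1 × (1 − 0.7³) = 0.0657. Then (1 − 0.0875)^10 = 40% and (1 − 0.0657)^10 = 51%.

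Under independence the result also moves with the assumed rate:
- At 5%: 0.95^30 = 21% asked directly, against 0.975^30 = 47% to 0.985^30 = 64%.
- At 20%: 0.80^30 = 0.1%, against 0.90^30 = 4% to 0.94^30 = 16%.

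The direction is the same in every scenario, but the size depends on figures that the documents do not supply.

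**The case against.** The plan does provide for enquiry. Adverse events are marked at every visit and at follow-up, section 6.3.2.1 has illnesses recorded at Visits 1 to 6, and the duty to log events is not tied to visits. A subject may report at any time, staff are present for about 4.5 h, and nausea is asked directly. With one drink per week, a recorded event can be attributed to a drink. Tolerability is not an aim or endpoint, and no tolerability conclusion is planned. Part of the appendices, the Appendix B figures, the case report form and the participant information were not available for review, so a lower-gut item may exist there.

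Most of this stands. A reader might infer that lower-gut intolerance will simply be missed, or recorded only a week later. The documents do not support that, for the reasons just given. Nor do they show that symptoms mostly begin after discharge: no transit or onset time is given, and the design itself looks for distal effects within three hours of the drink.

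What remains is narrower. The documents do not say how adverse events are elicited. The text and Table 1 disagree on whether illnesses are recorded at Visits 1 to 6. The visit list in section 6.3.2.1 omits adverse events. Section 7.1.1 defines an adverse event by reference to a pharmaceutical product, whereas section 2.1 classes the capsules as food, so it is unclear whether cramps after a drink would be logged. General enquiry is planned, but a specific question is not.

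**Conclusion.** The point holds as a modest gap in safety data collection. No readable form names lower-gut symptoms. After discharge, such symptoms rest on non-specific enquiry at the next weekly visit or on self-report, and for 17% of exposures on a follow-up with no date. Under-reporting or late recall is therefore possible.

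Its size cannot be computed from the documents, and neither can the share of symptoms arising after discharge. The contrast of 4% with 21% to 40% should not be cited as a finding: it needs an assumed symptom rate, an assumed capture rate and independent drinks, and under full clustering it shrinks to 35% against 40% to 51%. Nothing here affects the appetite, hormone or food-intake comparisons. The case for acting is that the remedy is cheap and gives better information than a general question.

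**What to change.** - Add a one-page tick list (abdominal pain, bloating, diarrhoea, vomiting, other) covering the 24 hours after each drink. Subjects complete it at home and return it at the next visit before the next drink. The window fits the existing request in the Summary to avoid alcohol and strenuous exercise for 24 hours after each study day.
- Give the follow-up after Visit 6 a date in Table 1 and collect the last list then.
- Tabulate the responses descriptively by drink, without formal testing.
- Name possible gastrointestinal upset from the drinks in section 3, and check that the participant information agrees.
- Reconcile sections 6.3.2.1 and 6.4.2 with Table 1 on recording illnesses at Visits 1 to 6.

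The cost is one extra form per visit (up to 10 × 6 = 60), one dated contact per subject (10) and a short amendment, all within existing staffing. Next-day calls are optional.

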Data will be analysed using GraphPad Prism (version 6.0) for Windows, GraphPad software (San Diego, CA, USA) and SPSS® (version 20.0) software (SPSS, Chicago, IL, USA). Central tendencies for patient and control group demographics, anthropometric data, caloric intake, VAS scores, QoL scores and macronutrient intake will be calculated and expressed using arithmetic mean \pm standard error of the mean or median (range), as appropriate. Differences in continuous variables between surgical and control groups will be calculated using the Student's *t* test or Mann-Whitney U test for parametric or non-parametric data, respectively. Correlative analyses will be performed using the Spearman Rho rank correlation to assess the relationship between *ad libitum* caloric intake and macronutrient intake with peri-operative weight loss and anthropometric data. Univariate analysis of factors associated with perioperative and post-surgical weight loss will be performed using Student's *t* test or one-way ANOVA for categorical variables or simple logistic regression for continuous variables. For the multivariate analysis, independent variables which were significant on univariate analysis, including standard demographic, oncologic and operative parameters as well as food intake and food preference, will be entered into a multiple logistic regression model with a forward stepwise selection procedure to assess their impact on perioperative and post-surgical weight loss. All statistical analyses will be two-tailed with the threshold of significance set at $P < 0.05$. Caloric intake and visual-analogue scores within groups will be compared by the Wilcoxon signed rank, matched-pairs test. Areas under the curve and plasma hormone levels will be compared by Wilcoxon rank-sum analysis.

12 Duration of Project

The estimated duration of the study will be 12 months. Screening and recruitment will begin in May 2017. Completion of the study is planned for May 2018.

13 Administrative considerations

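### Section 11 has no test of whether the distal-minus-stomach effect differs between protein, fat and carbohydrate, so the data analysed as planned could not support a protein-specific conclusion

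*Combined protocol and SAP*

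**What the plan says.** The six drinks listed under Methods in section 1 are high-protein, high-fat and high-carbohydrate mixed meals, each in a capsule that opens either in the stomach or in the distal small bowel. That is a 3 x 2 layout, and section 5.2 has every subject take all six.

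The documents state the question in two ways.

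- **Protein.** The Overview (section 2) expects that "altered exposition of the proximal small bowel to high protein microcapsules will increase satiety" and that this "would help developing natural protein formulas that would induce maximal anorexic effect". The formal hypothesis in section 4 is that "The delivery of high protein supplement to the proximal and distal gut will increase the release of anorexigenic gut hormones". The Conclusion in section 1 speaks of the "physiological function of protein supplement on increasing postprandial satiety, reducing appetite and food intake".
- **All macronutrients.** The goal at the end of section 2.1 is to learn "the physiological role of protein, fat, and carbohydrate content of the ingested food on specific gut hormone secretion". The primary aim (5.1) concerns the response "when macronutrients are digested in the distal rather than proximal small bowel". The hypothesis in section 1 is also about mixed meals in general.

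For the analysis, section 11 says "Caloric intake and visual-analogue scores within groups will be compared by the Wilcoxon signed rank, matched-pairs test". Areas under the curve and hormone levels get a rank-sum test. The threshold is two-tailed P < 0.05, with no multiplicity rule. The only ANOVA is one-way, and it and the regression models concern weight loss around surgery. Section 11 has no model of the six conditions, no macronutrient-by-site interaction and no difference-of-differences contrast.

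**The concern.** To say something specific about protein in a trial with three distal/stomach pairs, one must show that the distal effect for protein differs from the distal effect for fat and for carbohydrate. Nothing in section 11 estimates that difference. A reader who wants it has two substitutes:

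- compare three separate verdicts and note that protein crossed P < 0.05 while another macronutrient did not;
- compare the distal protein drink directly with the distal fat or carbohydrate drink.

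The first is not a test of a difference, because equal true effects will often give unequal verdicts at n=10. The second carries any effect that composition has regardless of site, so it does not isolate the effect of moving digestion distally.

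At stake is whether a general effect of distal delivery is taken for a property of protein. The Overview links the work to protein formulas, so this reading is foreseeable.

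**Working it through.** **Inputs.** From section 5.5: n=10, 80% power, alpha 0.05, with ad libitum energy intake as endpoint. From section 11: two-tailed P < 0.05 and the signed-rank test for intake and VAS. Assumed here, because the documents do not give them: the size of the distal effect, and the correlation rho (0 to 0.5) between one subject's distal-minus-stomach differences for two macronutrients.

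**1. The plan's own figure.** Section 5.5 gives no effect size, SD or named comparison, so n=10 cannot be reproduced. Solved backwards as a two-sided paired t test, n=10 has 80% power when the mean difference divided by the SD of the differences is 0.996. I use this as the reference effect for one pair.

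**2. Split verdicts when all three distal effects are equal (independent tests, power p each).**

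- Protein significant, at least one other not: p(1-p²). At p=0.8: 0.8 x 0.36 = 28.8%. At p=0.5: 0.5 x 0.75 = 37.5%.
- Protein alone significant: p(1-p)². At p=0.8: 0.8 x 0.04 = 3.2%. At p=0.5: 0.5 x 0.25 = 12.5%.

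**3. Allowing for the same ten subjects in all pairs.** The signed-rank test was simulated at n=10 (20,000 runs per row, normal differences, equal true effects). The last column is the false-positive rate of a signed-rank test applied directly to one difference of differences.

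| rho | Power per pair | Protein significant, at least one other not | Protein alone | Direct test of one contrast |
|---|---|---|---|---|
| 0 | 78% | 31% | 4% | 5.0% |
| 0 | 49% | 37% | 13% | 4.8% |
| 0.5 | 79% | 21% | 4% | 4.8% |
| 0.5 | 49% | 27% | 9% | 5.1% |

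The direct-test figure is for one contrast. With two contrasts, the chance that at least one is falsely significant is at most about 2 x 5% = 10%, and the chance that both are is at most about 5%.

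**4. What a direct contrast can detect at n=10.** The SD of (protein distal - protein stomach) - (fat distal - fat stomach) is sqrt(2(1-rho)) times the SD of one pair's difference: 1.41 at rho 0, 1.22 at 0.25 and 1.00 at 0.5. An interaction as large as the reference site effect therefore has a standardised size of 0.996/1.41, 0.996/1.22 or 0.996/1.00.

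| rho | Power, interaction as large as site effect | n for 80% | Power, half that size | n for 80% |
|---|---|---|---|---|
| 0 | 51% | 18 | 17% | 66 |
| 0.25 | 63% | 14 | 21% | 50 |
| 0.5 | 80% | 10-11 | 29% | 34 |

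The same figures apply to the protein-carbohydrate contrast.

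**The case against.** The strongest reply is that the protocol makes no comparative claim for protein. The sentence in the Conclusion says what the study will inform on; it does not say that protein outperforms fat or carbohydrate. The section 4 hypothesis is not comparative either, and the primary aim with its three objectives can be read as distal versus proximal delivery in general. This stands. A reader might infer that the plan intends to declare protein superior, and the documents do not support that. "Protein supplement" is itself a little ambiguous, because the capsule shell is also protein, although sections 2 and 4 do say high protein.

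Second, section 11 names no pairs for the signed-rank test, so one cannot say that it prescribes three distal-versus-stomach verdicts. This also stands. The gap remains whichever pairs are chosen, since no two-drink comparison estimates a difference between distal effects.

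Third, a reader might infer that equal effects would usually look protein-only. They would not: protein alone significant is a 3-4% event near 80% power, no more than the usual error rate, and 9-13% near 50%. The larger percentages include trials in which protein and one other macronutrient are both significant.

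Fourth, much of section 11 describes a surgical study, so the missing interaction is one part of a wider lack of analysis for the six-way crossover. That is fair, but a replacement analysis could still omit this term unless it is asked for.

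**Conclusion.** The point holds as a gap in the plan. The design and the goal in section 2.1 raise the question of macronutrient by site, the hypotheses and conclusion lean on protein, and section 11 cannot answer whether the distal effect differs by macronutrient.

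If the true effects are equal, judging by separate P values would suggest that protein differs from at least one other macronutrient in about 21-37% of trials, over power of roughly 50-80% and rho of 0 to 0.5. The stricter protein-alone pattern runs from about 3% to 13%. All these figures depend on assumed effect sizes and correlations, because section 5.5 gives neither a difference nor an SD. The 50% case is an assumption; 80% is the only power that the plan states, and for ad libitum intake only.

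**What to change.** For each endpoint, pre-specify two within-subject contrasts:

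- (protein distal - protein stomach) - (fat distal - fat stomach);
- (protein distal - protein stomach) - (carbohydrate distal - carbohydrate stomach).

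They can come, for example, from a mixed model with macronutrient, site, their interaction and period, and subject as random effect. Report each with its 95% CI. Allow a protein-specific conclusion only if both contrasts support it. Otherwise word the conclusion around distal versus proximal delivery of mixed meals, as the section 1 hypothesis and the primary aim already do.

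The two contrasts should stay separate. Setting protein against the average of fat and carbohydrate would not enforce the rule: with distal effects of 1, 1 and 0, that contrast equals 1 - 0.5 = 0.5 although protein and fat are identical.

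The cost is SAP text and two estimates per endpoint, with no added visits, samples or subjects. The downside is real: a protein-specific claim becomes harder to make. If one pair has 80% power, each contrast has only 51-80% power for an interaction as large as the site effect, and 17-29% for one half that size. Requiring both lowers the chance of a positive claim further. The SAP should therefore state that a non-significant contrast is not evidence of equal effects.
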